9.3. Safety Evaluations

Details regarding the IDMC are provided in Section 11.8.

Safety and tolerability will be evaluated throughout the study from signing of the ICF onwards until the last study-related activity.

Any clinically relevant changes occurring during the study must be recorded in the Adverse Event section of the eCRF.

Any clinically significant abnormalities persisting at the end of the study/early withdrawal will be followed by the investigator until resolution or until a clinically stable endpoint is reached.

The study will include the following evaluations of safety and tolerability according to the time points provided in the [TIME AND EVENTS SCHEDULE](#):

9.3.1. Adverse Events

Adverse events (including influenza complications) will be reported by the subject (or, when appropriate, by a caregiver, surrogate, or the subject's legally acceptable representative) for the duration of the study. Adverse events will be followed by the investigator as specified in Section 12, Adverse Event Reporting.

Special attention will be paid to those subjects who discontinue the study for an AE, or who experience an AE of at least grade 3, or an SAE.

9.3.2. Clinical Laboratory Tests

Blood samples for serum chemistry and hematology and a random urine sample for urinalysis will be collected. The investigator must review the laboratory report, document this review, and record any clinically relevant changes occurring during the study in the Adverse Event section of the eCRF. The laboratory reports must be filed with the source documents.

If feasible, safety blood samples will be collected after fasting for at least 10 hours.

In case a **grade 3** or **grade 4** laboratory abnormality occurs, a confirmatory test may be performed, preferably within 48 hours but no later than 72 hours after the results have become available.

The following tests will be performed by the central laboratory:

- Hematology Panel

-hemoglobin	-WBC differential
-hematocrit	*neutrophils
-red blood cell (RBC) count	*lymphocytes
-RBC parameters	*monocytes
*mean corpuscular hemoglobin (MCH)	*eosinophils
*MCH concentration	*basophils
*mean corpuscular volume	-platelet count
-white blood cell (WBC) count	

A WBC evaluation may include any abnormal cells, which will then be reported by the laboratory. Any RBC evaluation may include abnormalities in the RBC count and/or RBC parameters and/or RBC morphology, which will then be reported by the laboratory.

- Serum Chemistry Panel

-sodium	-uric acid
-potassium	-eGFR
-chloride	-calcium
-bicarbonate	-calcium (corrected for albumin)
-blood urea nitrogen (BUN)	-phosphate
-creatinine	-serum albumin
-glucose	-total protein
-AST	-total cholesterol
-ALT	-high-density lipoprotein cholesterol
-GGT	-low-density lipoprotein cholesterol
-total, direct, and indirect bilirubin	-triglycerides
-ALP	-magnesium
-CPK	-lipase
-lactic acid dehydrogenase (LDH)	-pancreatic amylase
	- α_1 -acid glycoprotein

- Urinalysis

Dipstick	Sediment (if dipstick result is abnormal)
-specific gravity	-RBCs
-pH	-WBCs
-glucose	-epithelial cells
-protein	-crystals
-blood	-casts
-ketones	-bacteria
-bilirubin	
-urobilinogen	
-nitrite	
-leukocyte esterase	

In case the dipstick shows 4+ (or >1.0%) proteinuria, a confirmatory test must be performed preferably within 48 hours but no later than 72 hours after the results have become available. If dipstick result is abnormal, flow cytometry or microscopy will be used to measure sediment. In case of discordance between the dipstick results and the flow cytometric results, the sediment will be examined microscopically.

Dipstick and flow cytometric analysis of the urine samples will be performed in parallel, ie, in the same sample at the same time.

- At screening, at Day 5, and at the Final Study Visit/Safety Follow-up Visit, a urine pregnancy test will be performed for female subjects of childbearing potential only.

- At screening, follicle-stimulating hormone (FSH) will be tested for female subjects who are amenorrheic for 12 months or less.
- At screening, hepatitis A, B, and C serologic testing will be performed.
- At screening and at the time points indicated in the [TIME AND EVENTS SCHEDULE](#), determination of the following coagulation parameters will be performed: prothrombin time (PT), activated partial thromboplastin time (aPTT), and fibrinogen. International normalized ratio (INR) will be calculated.

9.3.3. Electrocardiogram

During the collection of ECGs, subjects should be in a quiet setting without distractions (eg, television, cell phones). Subjects should rest in a supine position for at least 5 minutes before ECG collection and should refrain from talking or moving arms or legs. If blood sampling or vital sign measurement is scheduled for the same time point as ECG recording, the procedures should be performed in the following order: ECG, vital signs, blood draw. A historical ECG within 1 day before signing of the ICF can be used in lieu of the baseline ECG requirement.

Twelve-lead ECGs will be recorded so that the different ECG intervals (PR, QRS, and QT) and heart rate will be measured. The QT intervals will be corrected for heart rate according to Bazett's (QTcB) and Fridericia's (QTcF) QT correction.^{5, 10}

Clinically relevant abnormalities occurring during the study should be recorded in the Adverse Event Section of the eCRF.

9.3.4. Vital Signs (temperature, pulse/heart rate, respiratory rate, blood pressure, blood oxygen saturation, level of consciousness)

Vital signs including temperature, pulse/heart rate, respiratory rate, blood pressure, peripheral arterial blood oxygenation, and level of consciousness will be assessed once daily at screening and at the Final Study Visit/Safety Follow-up Visit. Vital signs will be assessed at least 3 times daily until the subject is discharged from the hospital or until Day 14 (whichever comes first): in the morning (prior to study drug intake if applicable), approximately half-way in the middle of the day, and in the evening (prior to study drug intake if applicable). If the subject is discharged from the hospital, vital signs will be measured once daily on Day 5 and Day 10, if practically feasible. In case, per standard practice, vital signs are measured more frequently than required per protocol, these additional measurements will also be recorded in the eCRF.

Temperature will be measured orally.

Blood oxygen saturation will be measured using standard pulse oximeter. Subjects should have nail polish removed and should be encouraged to sit still during the measurements.

Blood pressure, pulse/heart rate, and respiratory rate measurements should be preceded by at least 5 minutes of rest in the supine position in a quiet setting without distractions (eg, television, cell phones).

Blood pressure, pulse/heart rate, respiratory rate, and temperature measurements will be assessed with a completely automated device. Manual techniques will be used only if an automated device is not available.

The level of consciousness will be measured according to the AVPU scale (alert, voice, pain, unresponsive).⁸ Alert: The patient is fully awake (although not necessarily oriented). This patient will have spontaneously open eyes, will respond to voice (although may be confused), and will have bodily motor function. Voice: The patient makes some kind of response when you talk to them, which could be in any of the 3 component measures of eyes, voice, or motor. The response could be as little as a grunt, moan, or slight move of a limb. Pain: The patient makes a response on any of the 3 component measures on the application of pain stimulus, such as a central pain stimulus (sternal rub) or a peripheral stimulus (squeezing the fingers). Unresponsive: Sometimes seen noted as 'Unconscious'; this outcome is recorded if the patient does not give any eye, voice or motor response to voice or pain. The National Early Warning Score (NEWS) will be derived based on vital signs and AVPU scale at baseline and during hospitalization.¹²

Clinically relevant abnormalities (as defined in [Attachment 7](#)) occurring during the study should be recorded in the Adverse Event Section of the eCRF.

9.3.5. Physical Examination

To evaluate the subject's eligibility, a physical examination (including height and body weight measurement if not already available and if practically feasible) will be performed at screening. In addition, a symptom-directed physical examination will be performed at the time points provided in the [TIME AND EVENTS SCHEDULE](#).

A physical examination includes a review of the following systems: head/neck/thyroid; eyes/ears/nose/throat (EENT); respiratory; cardiovascular; lymph nodes; abdomen; skin; musculoskeletal; and neurological. Breast, anorectal, and genital examinations will be performed when medically indicated.

To obtain the actual body weight, subjects must be weighed lightly clothed. The height should be measured barefoot.

Any clinically relevant changes occurring during the study must be recorded in the Adverse Event Section of the eCRF.

9.3.6. Specific Toxicities

Subjects reporting allergic reactions, AST/ALT elevations, clinical hepatitis, renal complications, nausea, or diarrhea, and other laboratory parameter changes should be followed until resolution of the AE or toxicity and necessary standard management should be undertaken.

Refer to Section [10.2](#) for study drug discontinuation criteria.

Acute Systemic Allergic Reaction

Cetirizine, levocetirizine, topical corticosteroids or antipruritic agents may be prescribed.

Subjects should be advised to contact the investigator immediately if there is any worsening of the acute systemic allergic reaction.

Subjects will be treated as clinically appropriate.

AST and ALT Elevation

Subjects should be followed until resolution (return to baseline) or stabilization of AST/ALT elevation (to be agreed upon with the sponsor).

Clinical Hepatitis

Subjects taking the study drugs should be monitored for the development of signs and symptoms of hepatitis which include fatigue, malaise, anorexia, nausea, dark urine and clay-colored stools, bilirubinuria, jaundice, liver tenderness, or hepatomegaly, with or without initially abnormal serum transaminase levels.

Subjects with these signs and symptoms must seek medical attention immediately and have hepatic parameters assessed. Relevant markers of viral hepatitis should also be assessed.

Renal Complications

If renal complications develop, subjects should be closely monitored for disturbances in serum creatinine and for abnormalities in urine analysis (eg, proteinuria). Additional investigations can be performed at the investigator's discretion. Subjects must be treated as clinically appropriate.

Nausea (with or without Vomiting)

Subjects may be treated as needed with antiemetics given orally or rectally. The date and time of this AE should be recorded.

Diarrhea

Loperamide can be administered.

Other Laboratory Parameter Changes

If one (or more) of the following changes occurs, the subject should discontinue study drug and should be followed until resolution (return to baseline) or stabilization of change (to be agreed upon with the sponsor). The sponsor should be informed even if the change occurs outside of the treatment period (but before the end of the study).

- Liver enzymes - *screening/baseline*
 - AST or ALT enzyme activity increases ≥ 5 x ULN
 - Direct bilirubin increases ≥ 2 x ULN
 - GGT and/or ALP enzyme activity increases ≥ 3 x ULN

- Liver enzymes - *during treatment*
 - AST or ALT enzyme activity increases ≥ 5 x ULN if the baseline value is normal
 - AST or ALT enzyme activity increases ≥ 5 x baseline if the baseline value is $>ULN$
 - ALT enzyme activity increases >15 x ULN
 - ALT enzyme activity increases >3 x ULN and total bilirubin increases >2 x ULN
- Confirmed absolute neutrophil count $<500/mm^3$
- Hemoglobin <9 g/dL (female), <10.5 g/L (male)

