- Subject requires hospitalization to treat influenza infection and/or to treat complications of influenza infection.
- Subject tested positive for influenza A infection within 1 day of signing of the informed consent form (ICF) using a PCR-based rapid molecular diagnostic assay.
- Subjects must be capable of swallowing study medication tablets and capsules.
- Male or female subject, 18 to 85 years of age (extremes included).

Key Exclusion Criteria

- Subject received more than 3 doses of the influenza antiviral medication oseltamivir, zanamivir, or peramivir since the start of the influenza symptoms, or ribavirin within 6 months prior to screening.
- Subject is unwilling to undergo regular nasal MT swabs or has any physical abnormality which limits the ability to collect regular nasal specimens.
- Subject is known (considering lab results of the past 6 months) to be severely immunocompromised as defined by a CD4+ count <350 cells/mm³ or an absolute neutrophil count <750/mm³.
- Subject is undergoing peritoneal dialysis, hemodialysis, or hemofiltration.
- Subject has an estimated glomerular filtration rate (eGFR) ≤ 30 mL/min/1.73 m² according to the Modification of Diet in Renal Disease (MDRD) equation, assessed at screening or based on the most recent clinically relevant creatinine value if available.
- Subject has known moderate (Child-Pugh class B) or severe hepatic impairment (Child-Pugh class C).

DOSAGE AND ADMINISTRATION

During the treatment period, all subjects will receive 1 of the following 2 dose regimens:

- JNJ-63623872 600 mg bid + oseltamivir 75 mg bid on Days 1 through 7; OR
- JNJ-63623872 placebo bid + oseltamivir 75 mg bid on Days 1 through 7.

Note: For subjects who receive only 1 dose on Day 1 (evening), dosing should continue until the morning of Day 8 so that all subjects receive 14 doses in total.

Oseltamivir dose should be reduced to 30 mg bid for subjects with an eGFR >30 and ≤ 60 mL/min/1.73 m² according to the MDRD equation. Dose can be adjusted from 30 mg to 75 mg and vice versa during the course of treatment based on the eGFR value.

All study drugs will be taken orally. All subjects will take 2 tablets (JNJ-63623872 or placebo) and 1 capsule (oseltamivir) bid.

PHARMACOKINETIC EVALUATIONS

All evaluations will be performed as specified in the Time and Events Schedule.

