4.2. Exclusion Criteria

Any potential subject who meets any of the following criteria will be excluded from participating in the study.

1. Subject received more than 3 doses of the influenza antiviral medication oseltamivir, zanamivir, or peramivir since the start of the influenza symptoms, or ribavirin within 6 months prior to screening.
2. Subject is unwilling to undergo regular nasal MT swabs or has any physical abnormality which limits the ability to collect regular nasal specimens.
3. Subject is known (considering lab results of the past 6 months) to be severely immunocompromised as defined by a CD4⁺ count <350 cells/mm³ or an absolute neutrophil count <750/mm³.
4. Subject is undergoing peritoneal dialysis, hemodialysis, or hemofiltration.
5. Subject has an eGFR \leq 30 mL/min/1.73m² according to the MDRD equation, assessed at

screening or based on the most recent clinically relevant creatinine value if available.

6. Subject has known moderate (Child-Pugh class B) or severe hepatic impairment (Child-Pugh class C).
7. Subject has presence of any pre-existing illness, clinically significant laboratory abnormalities, ECG findings, or physical examination findings that, in the opinion of the investigator, would place the subject at an unreasonably increased risk through participation in this study. The investigator should consider the laboratory parameter criteria for study drug discontinuation (see Section 9.3.6) when screening a subject for enrollment.
8. Subject with known acute hepatitis A, B, or, C virus infection at screening, or known chronic hepatitis C infection undergoing antiviral therapy.
9. Subject has known allergies, hypersensitivity, or intolerance to JNJ-63623872 or its excipients (refer to the Investigator's Brochure⁶).
10. Subject has contraindications to the use of oseltamivir per local prescribing information.^{14,15}
11. Subject has received an investigational drug (including investigational vaccines) or used an invasive investigational medical device within 30 days, or has received an investigational biological product within 3 months or 5 half-lives (whichever is longer) before the planned first dose of study drug or is currently enrolled in an investigational study.
12. Subject has a history of clinically significant heart arrhythmias, eg, unstable angina or myocardial infarction; uncontrolled, unstable atrial arrhythmia, or sustained ventricular arrhythmia, or a history of risk factors for Torsade de Pointes syndrome.

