13. Subject has taken any disallowed therapies as noted in Section 8, Pre-study and Concomitant Therapy before the planned first dose of study drug.
14. Subject is an employee of the investigator or study site, with direct involvement in the proposed study or other studies under the direction of that investigator or study site, or a family member of an employee or the investigator, or an employee of the sponsor.
15. Female subject who is pregnant, or breastfeeding, or planning to become pregnant while enrolled in this study or within 90 days after the last dose of study drug, or female subject of childbearing potential who is unwilling to use an acceptable method of contraception as outlined in Section 4.3, Prohibitions and Restrictions.
16. Male subject who plans to father a child while enrolled in this study or within 90 days after the last dose of study drug.

17. Subject has any condition for which, in the opinion of the investigator, participation would not be in the best interest of the subject (eg, compromise the well-being) or that could prevent, limit, or confound the protocol-specified assessments.

NOTE: Investigators should ensure that all study enrollment criteria have been met at screening. If a subject's clinical status changes (including available laboratory results or receipt of additional medical records) after screening but before the first dose of study drug is given such that he or she no longer meets all eligibility criteria, then the subject should be excluded from participation in the study. Section 17.4, Source Documentation, describes the required documentation to support meeting the enrollment criteria.

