10.2. Discontinuation of Study Treatment

If a subject's study treatment must be discontinued before the end of the treatment regimen, this will not result in automatic withdrawal of the subject from the study.

A subject's study treatment should be discontinued if:

- The investigator believes that for safety reasons (eg, AE) it is in the best interest of the subject to discontinue study treatment
- The subject becomes pregnant
- The subject undergoes mechanical ventilation
- The subject requires peritoneal dialysis, hemodialysis, or hemofiltration
- The subject has an eGFR ≤ 30 mL/min/1.73 m² according to the MDRD equation
- The subject experiences any of the laboratory abnormalities as specified in Section [9.3.6](#), Specific Toxicities.

If a subject prematurely discontinues study treatment, follow-up assessments should be obtained and scheduled assessments should be continued. If a subject drops out due to withdrawal of consent, he or she will be offered an optional Safety Follow-up Visit.

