17.4. Source Documentation

At a minimum, source documentation must be available for the following to confirm data collected in the eCRF: subject identification, eligibility, and study identification; study discussion and date of signed informed consent; dates of visits (including telephone follow-up calls, if applicable); results of safety and efficacy parameters as required by the protocol; record of all AEs and follow-up of AEs; concomitant medication; drug receipt/dispensing/return records; study drug administration information; and date of study completion and reason for early discontinuation of study drug or withdrawal from the study, if applicable.

In addition, the author of an entry in the source documents should be identifiable.

At a minimum, the type and level of detail of source data available for a subject should be consistent with that commonly recorded at the study site as a basis for standard medical care. Specific details required as source data for the study will be reviewed with the investigator before the study and will be described in the monitoring guidelines (or other equivalent document).

The following data will be recorded directly into the eCRF and will be considered source data:

- Race
- History of smoking
- Blood pressure and pulse/heart rate
- Height and weight
- Details of physical examination

The PRO assessments (Flu-iiQ™, Flu-PRO and additional daily diary items) will be completed by subjects on an ePRO device. The results will be recorded directly into the ePRO database and will be considered source data.

The minimum source documentation requirements for Section 4.1, Inclusion Criteria and Section 4.2, Exclusion Criteria that specify a need for documented medical history are as follows:

- Referral letter from treating physician or
- Complete history of medical notes at the site
- Discharge summaries

Inclusion and exclusion criteria not requiring documented medical history must be verified at a minimum by subject interview or other protocol required assessment (eg, physical examination, laboratory assessment) and documented in the source documents.

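### Baseline liver values that should stop study drug are only something to consider at entry, so a subject known to exceed a limit can be randomized, dosed and then taken off treatment for that same value

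*Protocol*

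**What the plan says.** **Stopping.** In Section 9.3.6, under other laboratory parameter changes, the instruction is "If one (or more) of the following changes occurs, the subject should discontinue study drug". Two liver blocks follow. The first, labelled for screening/baseline, lists AST or ALT at or above 5 x ULN, direct bilirubin at or above 2 x ULN, and GGT or ALP at or above 3 x ULN. The second, labelled for the treatment period, sets limits relative to ULN or to baseline. Section 10.2 makes the list a reason to discontinue treatment: "The subject experiences any of the laboratory abnormalities as specified in Section" 9.3.6.

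**Entry.** Exclusion 7 in Section 4.2 covers clinically significant laboratory abnormalities that, in the investigator's opinion, add unreasonable risk. It then adds: "The investigator should consider the laboratory parameter criteria for study drug discontinuation (see Section 9.3.6) when screening a subject for enrollment". Exclusion 6 (known Child-Pugh B or C), Exclusion 8 (known acute hepatitis, or chronic hepatitis C under treatment) and Exclusion 17 (investigator's judgement) contain no enzyme or bilirubin limit.

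**Checks before dosing.** The note closing Section 4.2 excludes a subject whose clinical status changes "after screening but before the first dose of study drug is given such that he or she no longer meets all eligibility criteria". Section 17.4 adds: "Inclusion and exclusion criteria not requiring documented medical history must be verified at a minimum by subject interview or other protocol required assessment".

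**The concern.** The same three limits are an instruction to stop once the subject is on drug, but only advice when the subject is being enrolled. An investigator may see a value above a limit, judge the risk acceptable and enroll without breaking any criterion. Sections 9.3.6 and 10.2 then say that this subject should come off treatment, although nothing has changed since entry.

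That subject has been randomized and exposed to an investigational drug, and should then leave the randomized regimen on information available beforehand. Section 14.2 counts the oseltamivir capsules as study drug, so study oseltamivir stops too. The liver is a recognized concern for this compound: Section 1.4.3 lists transient transaminase elevations among its known risks, and Section 1.4.5 calls for close monitoring of liver enzymes.

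**Working it through.** There is no plan figure to reproduce. The check sets the stops that could be examined at entry beside the entry criteria.

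| Stop | Where | Numbered entry limit |
|---|---|---|
| Dialysis or hemofiltration | 10.2 | Exclusion 4, matching |
| eGFR <= 30 | 10.2 | Exclusion 5, same limit |
| Pregnancy | 10.2 | Exclusion 15, matching |
| Neutrophils < 500/mm3, confirmed | 9.3.6 | Exclusion 3, stricter: < 750/mm3, if known from the past 6 months |
| AST or ALT >= 5 x ULN at baseline | 9.3.6 | None; Exclusion 7, to consider |
| Direct bilirubin >= 2 x ULN at baseline | 9.3.6 | None; Exclusion 7, to consider |
| GGT or ALP >= 3 x ULN at baseline | 9.3.6 | None; Exclusion 7, to consider |
| Hemoglobin | 9.3.6 | None; Exclusion 7, to consider |
| Mechanical ventilation | 10.2 | None |

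The dialysis pair shows what alignment looks like: "Subject is undergoing peritoneal dialysis, hemodialysis, or hemofiltration" at entry and "The subject requires peritoneal dialysis, hemodialysis, or hemofiltration" as a stop. Four of the nine stops have a matching or stricter entry limit, and five do not. Of those five, only the three liver limits are themselves labelled for screening/baseline, so only they can already be met, by their own label, on the day of entry.

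**Worked case.** Take a known screening GGT of 3.5 x ULN, no known Child-Pugh B/C and no known hepatitis, in a subject whom the investigator judges not to be at unreasonable risk.

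1. Exclusions 6 and 8 are not met, and Exclusions 7 and 17 are not met on the investigator's judgement. The subject is eligible.
2. The Section 4.2 note and the Section 17.4 duty lead back to the same criteria, and so to the same judgement.
3. After the first dose, 3.5 >= 3, so the Section 9.3.6 baseline limit is met and treatment should stop under Section 10.2.

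**What the baseline block protects after dosing.** Write baseline ALT as b x ULN with b > 1. The on-treatment block stops at 5b x ULN or above, or when ALT exceeds 15 x ULN, whichever comes first.

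- b = 2: 5 x 2 = 10, so the stop is at 10 x ULN.
- b = 3: 5 x 3 = 15, so the stop is at 15 x ULN.
- b = 4: 5 x 4 = 20, so the cap governs and the stop is above 15 x ULN.
- b = 5: 5 x 5 = 25. The ALT stop is above 15 x ULN. AST has no cap, so its stop is at 25 x ULN.

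If the baseline block did not apply to a dosed subject with b = 5, no single-transaminase stop would act before those levels. Only the combined rule (ALT above 3 x ULN with total bilirubin above 2 x ULN) would remain. The on-treatment block has no GGT, ALP or direct bilirubin limit at all. The baseline block therefore has to stay in force whenever its result was seen.

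**The case against.** The best defence is that the entry link already exists and is deliberate. Exclusion 7 is itself a numbered criterion. It directs the investigator to Section 9.3.6 at screening, and the screening/baseline block is the obvious target. The Section 4.2 note mentions available laboratory results, so a new result before dosing has to be reassessed under Exclusion 7. Exclusion 17 gives a further ground to decline. The amendment log says that Exclusion 7 and the Section 9.3.6 rules were modified together in Amendment 3, and that toxicity management was updated for more severely ill inpatients. The block also has a sensible use: Section 9.3.2 sends these tests to a central laboratory and dosing is on Day 1, so a baseline result may arrive after the first dose.

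Most of this stands. It shows that there is protection, but of a discretionary kind. It does not remove the case of a value known before randomization. There the discretion achieves little, because whoever is admitted above a limit should then be stopped.

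A reader might infer more than the documents support:

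- *That entry has no liver safeguard.* Exclusions 6, 7, 8 and 17 all bear on it; what is missing is a firm limit.
- *That every other stop has a matching exclusion.* Hemoglobin and mechanical ventilation do not.
- *That the two liver blocks contradict each other.* They read coherently as a rule for the baseline sample and a rule for later samples.
- *That the baseline block could safely be limited to results first seen after dosing.* That would remove the stop for a subject dosed in error despite a value already seen.

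**Conclusion.** The gap is real but narrow. Three screening/baseline liver limits should stop treatment, and none is binding at entry. It arises only when the value is known before randomization, from a local result or a central one returned in time, and the investigator judges the risk acceptable.

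Its size cannot be given. The documents report no rate of entry values above these limits; Section 1.1 says only that ALT elevation has been described in influenza. A reader might infer a loss of precision for the primary PK comparison, since a subject stopped before Day 3 may not be PK-evaluable. With no rate to work from, that is not supported and is not claimed. Stopping treatment also does not mean leaving the study under Section 10.2. This is a cheap safety improvement that should be made, not a flaw that undermines the trial.

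**What to change.** Add one numbered exclusion to Section 4.2: AST or ALT >= 5 x ULN, direct bilirubin >= 2 x ULN, or GGT and/or ALP >= 3 x ULN. Give it the timing clause that the eGFR criterion already uses (Synopsis, key exclusion criteria; also Exclusion 5), "assessed at screening or based on the most recent clinically relevant creatinine value if available", with result in place of creatinine value. That form accepts an existing result, so sites need not wait for the central laboratory.

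Leave the screening/baseline block of Section 9.3.6 and all its limits as they are, applying to any dosed subject whenever the baseline result was seen. Exclusion 7 and Section 10.2 need no edit.

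The cost is one wording change in an amendment, a check of an existing liver result before randomization, and a few more screen failures. The investigator loses discretion over subjects whose enzymes are raised by influenza itself. Since those subjects should stop under the current text anyway, the exclusion mainly moves the decision to before randomization.
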